### **3.3 Safety Population**

The safety population will consist of all subjects who received any amount of study drug. Subjects in the Safety population will be analyzed as per actual treatment received.

## **4 DEFINITIONS**

### **4.1 Baseline**

Baseline is defined as the last value collected prior to the start of the study drug administration, unless specified otherwise. This usually is the value collected at Visit 1a Predose for vital signs, serum chemistry, hematology, and blood and urine biomarkers. If missing, then the value collected at unscheduled visit or Visit 0, whichever is available and more recent to study drug administration, will be used.

## 4.2 Study Day

To be consistent with the protocol definition, Study Day 1 is the day of the cardiac surgery. Study Days 2, 3, 4, 5, 6, 7, 30, 60 and 90 are the nominal days following Study Day 1.

## 4.3 Start/Stop Day

For adverse events or prior/concomitant medications, unless specified otherwise, the start day and the stop day are calculated from the date of the study drug administration.

Event day = event date – study drug administration date + 1 if the event is on/after study drug date, or

Event day = event date – study drug administration date if the event is before study drug date.

## 5 EFFICACY ENDPOINTS

### 5.1 Primary Efficacy Endpoint

The primary efficacy composite endpoint is defined as the geometric mean of the ratios of the maximum PreOp value (Visit 1b or Day 1 PreOp) over Baseline (Visit 1a) for the 3 preconditioning biomarkers,

$$Exp \left\{ \frac{1}{3} \cdot \left[ Log \left( \frac{\text{max PreOp HO-1}}{\text{Baseline HO-1}} \right) + Log \left( \frac{\text{max PreOp Ferritin}}{\text{Baseline Ferritin}} \right) + Log \left( \frac{\text{max PreOp IL-10}}{\text{Baseline IL-10}} \right) \right] \right\}.$$

For sensitivity analysis, this composite endpoint will also be defined as the geometric mean of the ratios of average of Day 1 PostOp through Day 3 over baseline for the 3 preconditioning biomarkers {HO-1, Ferritin, and IL-10}, where Avg (average) is calculated as the area under the biomarker-time curve (AUC) divided by the duration in the AUC calculation (AUC/D), and

$$AUC = \left\{ \sum_{i=2}^n (v_i + v_{(i-1)}) (t_i - t_{(i-1)}) \right\} / 2,$$

$$D = t_n - t_1$$

$v_1$  and  $v_n$  are the first (Visit 1b or Day 1 for subjects dosed 36 to 48 hours or 24 to <36 hours prior to surgery, respectively) and last (Study Day 3) biomarker values after study drug administration,  $t_i$  is the date and time of the  $i^{\text{th}}$  biomarker test.

Baseline for this composite endpoint is calculated as

$$(\text{Baseline HO-1} * \text{Baseline ferritin} * \text{Baseline IL-10})^{1/3}.$$

Because an increase in plasma biomarkers is beneficial and because the ratios are calculated as the follow-up value over the baseline value, a value >1 for the primary efficacy endpoint would indicate benefit.

## 5.2 Secondary Efficacy Endpoints

### 5.2.1 Maximum PostOp over Baseline in Renal Tubular Injury Biomarkers

The secondary efficacy composite endpoint is defined as the geometric mean of the ratios of the maximum PostOp value (Day 1, 1 hour post cardiac surgery through Day 3) over Baseline (Visit 1a) for the 3 tubular injury biomarkers,

$$\text{Exp} \left[ \frac{1}{3} * \left( \begin{aligned} & \text{Log} \left( \frac{\text{max(KIM-1 PostOp through Day 3)}}{\text{Baseline KIM-1}} \right) + \\ & \text{Log} \left( \frac{\text{max(CysC PostOp through Day 3)}}{\text{Baseline CysC}} \right) + \\ & \text{Log} \left( \frac{\text{max(NGAL PostOp through Day 3)}}{\text{Baseline NGAL}} \right) \right) \right]. \end{aligned} \right.$$

Baseline for this composite endpoint is calculated as

$$(\text{Baseline KIM-1} * \text{Baseline CysC} * \text{Baseline NGAL})^{1/3}.$$

Because a lack of increase in renal tubular injury biomarkers is considered beneficial and because the ratios are calculated as the follow-up value over the baseline value, a value >1 would indicate an increased risk.

This endpoint is expected to capture the kidney injury manifested by any of the 3 biomarkers at any time in the 3 days following the surgery.

### 5.2.2 Reduction in Urine Output

The reduction in urine output (documented AE of sustained reduction in urine output, oliguria, or anuria) post-cardiac surgery through Day 5 will be evaluated by the site and captured as an AE on the AE log eCRF.

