7.2 Secondary Objective

The secondary objectives are to evaluate the efficacy of RBT-1 on the following:

- Change in renal tubular injury biomarkers post-cardiac surgery through Day 3.
- Reduction in urine output (documented oliguria of <0.5 mL/kg/hour, not due to urinary tract obstruction or hypotension) for more than 6 hours post-cardiac surgery through Day 3.
- Incidence of AKI (defined using the modified KDIGO criteria) post-cardiac surgery through Day 5.

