9.7.4.2 Post-Cardiac Surgery

The following procedures will be performed post-cardiac surgery on Day 1:

- Record changes in concomitant medications.
- Measure urine output.
- Solicit any adverse events.

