### 5.2.3 Incidence of AKI

The incidence of AKI post-cardiac surgery through Day 5 will be defined as:

- An absolute increase from baseline to  $\geq 1.5 \times$  Baseline at any time; or
- A documented AE of sustained reduction in urine output, oliguria, or anuria; or
- Initiation of dialysis

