  - 2 Serum chemistry parameters include total protein, albumin, bicarbonate, blood urea nitrogen, serum creatinine, total bilirubin, alkaline phosphatase, glucose, sodium, potassium, phosphate, calcium, magnesium, gamma-glutamyl transferase, alanine aminotransferase, aspartate aminotransferase, and cystatin C.
  - 3 Serum ferritin is also to be assessed at Screening if not already included in local laboratory chemistry panel.
  - 4 Hematology parameters include red blood cell count [RBC], hemoglobin, hematocrit, mean corpuscular volume [MCV], mean corpuscular hemoglobin [MCH], mean corpuscular hemoglobin concentration [MCHC], platelets, mean platelet volume [MPV], red cell distribution width [RDW], white blood cell count [WBC], and WBC differential (including neutrophils [absolute and percentage], lymphocytes [absolute and percentage], monocytes [absolute and percentage], eosinophils [absolute and percentage], and basophils [absolute and percentage]).
  - 5 Urinalysis parameters include glucose, ketones, leukocytes, nitrite, blood, pH, protein, specific gravity, and reflex microscopic.
  - 6 Urine output will be measured through Day 3.
  - 7 Blood biomarkers include preconditioning response biomarkers (plasma heme oxygenase-1 [HO-1], ferritin, and interleukin-10 [IL-10]) and other biomarkers of RBT-1 activity and kidney function.
  - 8 Blood and urinary biomarkers will be collected within 4 hours prior to cardiac surgery.
  - 9 Urinary biomarkers include tubular injury biomarkers (kidney injury molecule-1 [KIM-1], cystatin C, and neutrophil gelatinase-associated lipocalin [NGAL]), and other biomarkers of RBT-1 activity and kidney function.
  - 10 A pregnancy test will be performed in female subjects of childbearing potential.
  - 11 RBT-1 and placebo will be administered via intravenous infusion over a 120-minute period.
  - 12 Adverse events assessment will include photosensitivity assessment.

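### The SAP analyses oliguria only as a site-reported AE through Day 5, so the protocol's rate-and-duration endpoint through Day 3 is not analysed although urine output is collected on Days 1 to 3

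*SAP*

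**What the plan says.** **Protocol.** Section 7.2 makes reduced urine output a secondary objective, specified as "documented oliguria of <0.5 mL/kg/hour, not due to urinary tract obstruction or hypotension" and lasting "for more than 6 hours post-cardiac surgery through Day 3". Section 11.1 gives the same rate, duration and window but names only obstruction as an exclusion. Section 9.7.4.2 tells sites to "Measure urine output" after surgery on Day 1, and Section 9.7.5 limits further measurement to Days 2 and 3.

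**SAP.** Section 5.2.2 replaces this with a "documented AE of sustained reduction in urine output, oliguria, or anuria", which "post-cardiac surgery through Day 5 will be evaluated by the site and captured as an AE on the AE log eCRF". Section 7.5.2.2 compares the resulting proportions by Fisher's exact test, each active group against placebo. Section 5.2.3 lists "A documented AE of sustained reduction in urine output, oliguria, or anuria" as one of three alternative criteria for AKI through Day 5, beside a rise to at least 1.5 times baseline and initiation of dialysis. The schedule in Appendix A still says "Urine output will be measured through Day 3". Section 1 gives the SAP precedence where the two documents differ.

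**The concern.** The protocol attaches a rate, a duration and exclusions to this endpoint and schedules a measurement to support it. The SAP attaches none of these. It does not define a sustained reduction, and its window runs two days past the last scheduled measurement. Two sites could classify the same urine record differently, and up to 20 sites in four countries take part.

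At stake is the interpretation of one secondary endpoint. If AE reporting misses events at a similar rate in every arm, the observable difference shrinks and power falls. Without an analysis of the collected data, a reader of the results could not judge how far a finding, or its absence, depends on reporting practice.

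**Working it through.** **1. The two definitions side by side**

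| | Protocol 7.2 and 11.1 | SAP 5.2.2 and 7.5.2.2 |
|---|---|---|
| Source | Documented oliguria, with urine output scheduled | AE log |
| Rate | Below 0.5 mL/kg/hour | None |
| Duration | More than 6 hours | Described as sustained, not defined |
| Exclusions | 7.2: obstruction and hypotension; 11.1: obstruction only | None |
| Window | Through Day 3 | Through Day 5 |
| Scheduled measurement | Days 1 to 3 | Days 1 to 3; none on Days 4 and 5 |

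SAP Appendix A adds that the Day 4 to 6 visits take place only if the subject is still in hospital.

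**2. Where the collected urine output goes.** In the current SAP Section 8, the urine-output table (14.2-3.2) and the corresponding listing (16.2-2.3.2) are both AE-based. The AKI sensitivity analyses in Section 7.5.2.3 use serum creatinine only. Section 7.2 promises in general terms that all data will be listed, but a listing is not an analysis. No current table or sensitivity analysis applies the protocol definition.

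**3. What under-capture would cost.** The plan gives no event rate or power for oliguria, so there is no figure to reproduce. The power statements in SAP Section 7.1 concern the two biomarker composites. The following is an illustration.

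Inputs from the documents: 42 per group (protocol synopsis), Fisher's exact test (SAP 7.5.2.2), two-sided 0.05 (SAP 7.2). Assumed inputs: true rates of 30% on placebo and 15% on active, and the share of true events that reach the AE log. Protocol Section 6.1 gives about 30% for AKI, not for oliguria.

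With no false positives, observed rate = capture × true rate. Power is the sum, over all pairs (i, j), of Bin(i; 42, placebo rate) × Bin(j; 42, active rate), counting only pairs whose Fisher p-value is at most 0.05.

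| Capture | Observed rates | Power |
|---|---|---|
| 100% | 0.300 vs 0.150 | 0.300 |
| 80% | 0.8 × 0.30 = 0.240 vs 0.8 × 0.15 = 0.120 | 0.224 |
| 50% | 0.5 × 0.30 = 0.150 vs 0.5 × 0.15 = 0.075 | 0.110 |

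Other assumed rates show the same pattern. For 30% vs 10%, power is 0.563, 0.432 and 0.203 at the same capture levels. For 50% vs 25%, it is 0.599, 0.436 and 0.237.

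False positives reduce it further. With 50% capture and 5% of non-events wrongly reported, the first scenario gives 0.5 × 0.30 + 0.05 × 0.70 = 0.185 against 0.5 × 0.15 + 0.05 × 0.85 = 0.1175, and power of 0.088.

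**4. What else depends on the AE.** Under SAP 5.2.3 the AE alone classifies a subject as having AKI. SAP 5.3.3 defines MAKE30, MAKE60 and MAKE90 for subjects with AKI through Day 5. A site's decision to record this AE can therefore change a subject's status for all of these endpoints.

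**The case against.** **The change is deliberate and disclosed.** SAP Appendix B sets the old and new definitions side by side, and Section 1 settles which one governs. That stands, and the point does not ask for the AE definition to be withdrawn. The gap is between the current protocol and the current SAP, and does not depend on superseded text.

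**AEs are not left to chance.** A reader might take these to be spontaneous reports. They are not: protocol Sections 9.7.4.2 and 9.7.5 have sites solicit AEs after surgery and daily to Day 7 or discharge, and SAP 5.2.2 has the site evaluate the event. What remains is that the solicitation is general, with no stated threshold or prompt for oliguria.

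**Misclassification is not demonstrated.** This also stands. The documents give no capture rate, specificity or oliguria rate, so they support only a liability to error of unknown size.

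**AKI need not lose power.** A reader might carry the power loss over to AKI. The protocol's AKI definition (Section 11.1) is creatinine-only, so the AE criterion can only add cases to the SAP's other two, and a subject missed by the AE log can still qualify on creatinine or dialysis. Section 7.5.2.3 already has creatinine-only sensitivity analyses at 0.3 and 0.5 mg/dL. What survives is dependence on the AE, and the lack of a version with only the 1.5-times-baseline and dialysis criteria.

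**A spurious drug effect does not follow.** The trial is randomised and double-blind and all arms share one definition. The documents give no mechanism by which the definition would create a difference between arms.

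**The measured data may be thin.** The only description of their capture, in the superseded text quoted in SAP Appendix B, is a site-assessed yes/no variable on the daily eCRF. If that is all the database holds, the added analysis compares two site assessments. It would still apply the stated rate and duration, which the AE does not.

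**Conclusion.** The point holds as an omission. The protocol-defined secondary endpoint is not analysed under the current SAP, although the protocol schedules the urine output to support it. The AE-based substitute has no rate or duration and covers two days without scheduled measurement. Its likely cost is power and interpretability in the urine-output endpoint, and AKI and the MAKE endpoints also depend on it.

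The size is unknown. The fall from 30% to 22% or 11% power rests on assumed rates of 30% and 15%, assumed capture, no false positives and the full 42 per arm, and it concerns oliguria alone. Power is low in that scenario even with complete capture, and the SAP claims none for this endpoint. The primary endpoint is not affected. The case for the change is that it is cheap and lets readers see how much the result depends on the source of the event.

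**What to change.** Keep the AE definition and add the following to the SAP before unblinding:

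1. A sensitivity analysis of protocol-defined oliguria through Day 3, using the Day 1 to 3 urine-output data as captured on the eCRF, with the same Fisher comparisons.
2. A cross-tabulation, by arm, of that result against AE-reported oliguria.
3. An AKI sensitivity analysis with the AE criterion removed, leaving creatinine of at least 1.5 times baseline or dialysis.

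Before programming, reconcile protocol Sections 7.2 and 11.1, which differ on whether oliguria due to hypotension is excluded. State also what the SAP means by a sustained reduction.

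The cost is SAP wording and a few extra tables, with no new procedures or subjects. The downside is that urine-output records may be incomplete, or held only as a site yes/no flag. If so, report the number of subjects with usable records and the form of the data beside the results.

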4 STUDY SYNOPSIS

Renibus Therapeutics, Inc.	Protocol No. REN-004
Name of Drug: RBT-1	Phase of Development: 2
Name of Active Ingredients: Stannous protoporphyrin (SnPP) and iron sucrose (FeS)	Date of Study Synopsis: 25 Aug 2022

Protocol Title: A Phase 2, Double-Blind, Randomized, Placebo-Controlled Study to Evaluate the Effect of RBT-1 on Preconditioning Response Biomarkers in Subjects Undergoing Coronary Artery Bypass Graft (CABG) and/or Cardiac Valve Surgery (The START Study)
	

Investigational Sites: Up to 20 sites in the United States, Canada, Australia, and New Zealand.
	

Study Objectives: The overall objective is to evaluate the effect of RBT-1 on preconditioning response biomarkers in subjects undergoing CABG and/or cardiac valve surgery.
 
Primary Objective The primary objective is to evaluate the efficacy of RBT-1 in generating a preconditioning response as measured by plasma biomarkers (heme oxygenase-1 [HO-1], ferritin, and interleukin-10 [IL-10]) from Baseline (pre-dose) through Day 1 pre-op.
 
Secondary Objectives The secondary objectives are to evaluate the efficacy of RBT-1 on the following:
 
 • Change in renal tubular injury biomarkers post-cardiac surgery through Day 3. • Reduction in urine output (documented oliguria of <0.5 mL/kg/hour, not due to urinary tract obstruction or hypotension) for more than 6 hours post-cardiac surgery through Day 3. • Incidence of acute kidney injury (AKI) (defined using the modified Kidney Disease Improving Global Outcomes [KDIGO] criteria) post-cardiac surgery through Day 5. 
Exploratory Objectives The exploratory objectives are to evaluate the following:
 
 • Severity of AKI post-cardiac surgery through Day 7. • Mean increase in serum creatinine post-cardiac surgery through Day 7 or until Discharge if prior to Day 7. • Occurrence of Major Adverse Kidney Events (MAKE) – death, need for dialysis, and persistent renal dysfunction – post-cardiac surgery through Day 30 (MAKE30) and Day 90 (MAKE90) post-cardiac surgery. • Proportion of subjects experiencing MAKE30. • Proportion of subjects experiencing MAKE90. • Days on ventilator. • Days in intensive care unit (ICU). • Hospital length of stay. • Readmission rate. • Changes in biomarkers of RBT-1 activity and/or kidney function. 	

Study Design:

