19. Treatment with an investigational drug or participation in an interventional study within 30 days prior to administration of study drug.
20. In the opinion of the Investigator, any disease processes or confounding variables that would inappropriately alter the outcome of the study.
21. Inability to comply with the requirements of the study protocol.

Drug, Dose and Mode of Administration:

RBT-1 will be supplied as a sterile liquid (in separate vials of SnPP and FeS) for IV injection and is intended for single use. Instructions for dose preparation will be specified in the Pharmacy Manual.

Commercially available 0.9% sodium chloride (normal saline) for injection will be used for placebo administration.

Study drug (low-dose RBT-1 [45 mg SnPP/240 mg FeS], high-dose RBT-1 [90 mg SnPP/240 mg FeS], or placebo [normal saline]) will be administered via IV infusion over a 120-minute period at ≥ 24 but ≤ 48 hours prior to scheduled cardiac surgery.

Study Duration:

Study duration is approximately 90 days per subject.

Criteria for Evaluation:

Efficacy assessments include the following:

- Change in preconditioning plasma biomarkers through Day 1 pre-op:
 - HO-1, ferritin, and IL-10.
- Change in renal tubular injury biomarkers post-cardiac surgery through Day 3:
 - Kidney injury molecule-1 (KIM-1), cystatin C, and neutrophil gelatinase-associated lipocalin (NGAL)
- Reduction in urine output (documented oliguria of < 0.5 mL/kg/hour, not due to urinary tract obstruction or hypotension) for more than 6 hours post-cardiac surgery through Day 3.
- Incidence of AKI post-cardiac surgery through Day 5, defined as:
 - An absolute increase in serum creatinine by 0.5 mg/dL, which is present over 2 laboratory measurements at least 12 hours apart; or
 - An increase in serum creatinine ≥ 1.5 X Baseline.
- Severity of AKI post-cardiac surgery through Day 7.
- Mean increase in serum creatinine post-cardiac surgery through Day 7 or until Discharge if prior to Day 7.
- Occurrence of MAKE30 and MAKE90 post-cardiac surgery.
- Proportion of subjects experiencing MAKE30.
- Proportion of subjects experiencing MAKE90.
- Days on ventilator.
- Days in ICU.
- Hospital length of stay.
- Readmission rate.
- Changes in biomarkers of RBT-1 activity and/or kidney function.

Safety assessments include the following:

- Adverse events
- Laboratory data and vital signs at regular intervals.

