11.1 Criteria for Evaluation

Efficacy assessments include the following:

- Change in preconditioning plasma biomarkers from Baseline (pre-dose) through Day 1 pre-op:
 - HO-1, ferritin, and IL-10
- Change in renal tubular injury biomarkers post-cardiac surgery through Day 3:
 - KIM-1, cystatin C, and NGAL

- Reduction in urine output (documented oliguria of <0.5 mL/kg/hour, not due to urinary tract obstruction) for more than 6 hours post-cardiac surgery through Day 3.
- Incidence of AKI post-cardiac surgery through Day 5, defined as:
 - An absolute increase in serum creatinine by 0.5 mg/dL, which is present over 2 laboratory measurements at least 12 hours apart; or
 - An increase in serum creatinine $\geq 1.5X$ Baseline.
- Severity of AKI post-cardiac surgery through Day 7.
- Average increase in serum creatinine post-cardiac surgery through Day 7 or until Discharge if prior to Day 7.
- Occurrence of MAKE30 and MAKE90 post-cardiac surgery.
- Proportion of subjects experiencing MAKE30.
- Proportion of subjects experiencing MAKE90.
- Days on ventilator.
- Days in intensive care unit.
- Hospital length of stay.
- Readmission rate.
- Changes in biomarkers of RBT-1 activity and/or kidney function.

Safety assessments include the following:

- Adverse events.
- Laboratory data and vital signs at regular intervals.

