**LIST OF LISTINGS**

Listing 16.2-2.1.1 Subject Preconditioning Response Biomarker Individual Test Results by Visit - MITT Population

Listing 16.2-2.1.2 Subject Preconditioning Response Biomarker Composite Score (Max PreOp/Baseline) - MITT Population

Listing 16.2-2.2.1 Subject Kidney Tubular Injury Biomarker Individual Test Results by Visit - MITT Population

Listing 16.2-2.2.2 Subject Kidney Tubular Injury Biomarker Composite Score (Max PostOp/Baseline) - MITT Population

Listing 16.2-2.3.2 Subject Sustained Urinary Retention During the First 5 Days Post Surgery Based on AE Report - MITT Population

Listing 16.2-2.4 Subject Serum Creatinine and eGFR Assessments by Visit - MITT Population

Listing 16.2-2.5.1 Subject Incidence of Acute Kidney Injury PostOp Through Day 5 - MITT Population

Listing 16.2-2.5.2 Subject Incidence and Severity of Acute Kidney Injury PostOp Through Day 7 - MITT Population

Listing 16.2-2.6 Subject Major Kidney Events Derivation - MITT Population

Listing 16.2-2.7 Subject Post Surgery Hospitalization Parameters - MITT Population

Listing 16.2-3.1 All Adverse Event Reports - Safety Population

Listing 16.2-3.2 Serious Treatment-Emergent Adverse Events - Safety Population

Listing 16.2-3.3 Treatment-Emergent Adverse Events Leading to Study Discontinuation - Safety Population

Listing 16.2-3.4 Treatment-Emergent Adverse Events with Outcome of Death - Safety Population

Listing 16.2-3.5.1 Subject Hematology Test Results by Visit - Safety Population

Listing 16.2-3.5.2 Subject Chemistry Test Results by Visit - Safety Population

Listing 16.2-3.5.3 Subject Urinalysis Test Results by Visit - Safety Population

Listing 16.2-3.5 Treatment-Emergent Adverse Events Drug Related - Safety Population

Listing 16.2-3.6 Subject Vital Signs by Visit - Safety Population

Listing 16.2-3.7 Subject Body Weight, Height, and BMI at Screening and End of Study - Safety Population

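### The SAP's urine-output endpoint, which alone can establish AKI, omits the protocol's exclusion of low output caused by urinary tract obstruction

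*SAP*

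**What the plan says.** **Protocol.** The synopsis, in its secondary objectives, defines the endpoint as "documented oliguria of <0.5 mL/kg/hour, not due to urinary tract obstruction or hypotension". Its criteria for evaluation repeat the condition: "not due to urinary tract obstruction or hypotension) for more than 6 hours post-cardiac surgery through Day 3". Section 7.2 carries the same two exclusions, "not due to urinary tract obstruction or hypotension". Section 11.1 keeps only one of them: "not due to urinary tract obstruction) for more than 6 hours post-cardiac surgery through Day 3". The protocol's AKI definition (synopsis and Section 11.1) rests on serum creatinine alone and has no urine-output criterion.

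**SAP.** Section 5.2.2 replaces the measured definition with a "documented AE of sustained reduction in urine output, oliguria, or anuria", recorded by the site on the AE log through Day 5. Sections 2.2 and 7.5.2.2 use the same rule. Section 5.2.3 lists "A documented AE of sustained reduction in urine output, oliguria, or anuria" as one of three alternative routes to AKI. AKI status then decides who is staged for severity (Section 5.3.1) and who can be counted for MAKE30, MAKE60 and MAKE90 (Section 5.3.3). None of these sections filters the AE by cause or provides for adjudication of cause. Section 1 states that the SAP prevails where it differs from the protocol.

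**Outputs.** Listing 16.2-2.3.2, which shows these events, is titled "Subject Sustained Urinary Retention During the First 5 Days Post Surgery Based on AE Report". Table 14.2-3.2, which summarises them, refers to urine reduction instead.

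**The concern.** Obstruction is the one cause that every current protocol definition of this endpoint removes. The SAP removes no cause. Since the SAP governs, an obstructive low-output episode recorded as oliguria, anuria or sustained reduction in urine output would count in the urine-output endpoint. Through Section 5.2.3 it would also count as AKI, even with unchanged creatinine.

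If such episodes are about equally frequent on active drug and placebo, they add the same background to both sides of each comparison. The risk difference shrinks, the risk ratio moves towards 1 and power falls. The extra AKI cases also become eligible for AKI staging and MAKE.

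This point concerns only which causes count. The SAP also changed the source of the data, the rate and duration thresholds and the day window. Restoring any of those would still leave cause unrestricted.

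**Working it through.** **Step 1: the cause rules side by side.**

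| Place | Obstruction excluded | Hypotension excluded | Counts as AKI by itself |
|---|---|---|---|
| Protocol synopsis, objectives | yes | yes | no |
| Protocol synopsis, criteria for evaluation | yes | yes | no |
| Protocol 7.2 | yes | yes | no |
| Protocol 11.1 | yes | no | no |
| SAP 2.2, 5.2.2, 7.5.2.2 (urine output) | no | no | – |
| SAP 2.2, 5.2.3 (AKI) | no | no | yes |

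The protocol is consistent on obstruction and inconsistent on hypotension. The SAP has neither exclusion, and it creates the link to AKI.

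**Step 2: is the loss made good elsewhere in the SAP?** Section 7.5.2.3 adds a sensitivity analysis of creatinine rises of at least 0.3 and at least 0.5 mg/dL, over two consecutive measurements at least 12 hours apart, through Day 5. It has no urine-output criterion, so it gives a partial check on AKI. It does not include an analysis of the 1.5-times-baseline criterion alone, and it does nothing for the urine-output endpoint. Appendix B records the change of definition but gives no reason for dropping the exclusion.

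**Step 3: illustration of size.** The documents state no power for either endpoint, so there is no figure of the plan's to reproduce.

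Inputs from the documents:
- 42 subjects per arm (protocol synopsis);
- Fisher's exact test (SAP 7.5.2.2 and 7.5.2.3), two-sided alpha 0.05 (SAP 7.2);
- AKI about 30% after cardiac surgery (protocol 6.1), used as the placebo rate.

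Assumptions:
- AKI 10% on active drug;
- urine-output events 15% on placebo and 5% on active drug;
- a fraction r of each arm, equal across arms and independent of true events, has an obstructive low-output AE recorded under one of the listed terms.

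The observed rate is p' = p + (1 − p)r. The observed difference is therefore (1 − r) times the true difference. For example, with r = 0.05 the placebo rate is 0.30 + 0.70 × 0.05 = 0.335 and the active rate is 0.10 + 0.90 × 0.05 = 0.145. The difference is 0.190 = 0.95 × 0.20. Power is exact, by summing over all pairs of event counts.

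| r | AKI, placebo vs active | Risk ratio | Power, AKI | Power, urine output (15% vs 5%) |
|---|---|---|---|---|
| 0 | 30.0% vs 10.0% | 0.33 | 56% | 20% |
| 1/42 = 2.4% | 31.7% vs 12.1% | 0.38 | 51% | 18% |
| 5% | 33.5% vs 14.5% | 0.43 | 46% | 16% |
| 10% | 37.0% vs 19.0% | 0.51 | 37% | 13% |
| 15% | 40.5% vs 23.5% | 0.58 | 31% | 11% |

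The lower rows are a stress range, not an expectation: 15% of 42 is about 6 subjects per arm. With AKI at 30% versus 15% instead, power falls from 30% at r = 0 to 25% at 5% and 20% at 10%.

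**The case against.** Several counter-arguments have force.

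- **Precedence is stated and the change is logged.** For programming there is one operative rule, the SAP's. That stands. It settles what will be analysed, but not whether the analysis measures the protocol's stated objective, and no reason for losing the exclusion is given.
- **Urinary retention is not an endpoint term.** From the listing title a reader might infer that every retention AE counts as AKI. The documents do not support this. The terms in SAP 5.2.2, 5.2.3 and 7.5.2.2 do not include retention. Appendix B shows that a listing deleted from SAP v2.0 also used the word, although v2.0 excluded obstruction. Table 14.2-3.2 speaks of urine reduction. The title is a label to correct, not evidence of a mapping rule.
- **The protocol never applied the exclusion to AKI.** A reader might also infer that the protocol classes hypotensive or obstructive low output as not AKI. It does not. Its exclusion belongs to the urine-output endpoint, its AKI definition is creatinine-only, and the KDIGO summary in Section 6.1 states a urine-volume criterion with no exclusion by cause. What stands is that the SAP moved a urine-output event into AKI without the filter that event carried in the protocol.
- **Hypotension is debatable.** It can arise after randomization and could differ between arms, so excluding events on a site-attributed cause could itself introduce bias. The protocol's sections also disagree. This review therefore asks only for reconciliation.
- **The size is assumed.** This is correct. The SAP's power statements cover the primary and tubular-injury endpoints, so no stated power is contradicted. The efficacy analysis of these endpoints also uses the MITT set, which may be smaller than 42 per arm.

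**Conclusion.** The point holds for obstruction. The SAP drops a filter that all current protocol definitions of the endpoint share, and the unfiltered AE then feeds a second secondary endpoint and, through AKI status, AKI severity and MAKE. Obstructive low output recorded under one of the listed terms can count; how often it would is unknown. With about one such subject per arm, the illustration loses about 5 percentage points of power for AKI (56% to 51%) and about 2 for urine output (20% to 18%). At 5% per arm the losses are about 11 and 4 points. These figures depend on the assumed event rates, on equal frequency in all arms and on 42 analysed per arm. If frequency differed by arm, the bias could go either way.

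On hypotension, the finding is limited to an inconsistency between the protocol synopsis and Section 7.2, protocol Section 11.1, and the SAP. The primary biomarker endpoint is not affected.

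**What to change.** 1. In SAP 2.2, 5.2.2, 5.2.3 and 7.5.2.2, count the AE only if it was not due to urinary tract obstruction. Settle cause by query to the site under blinded review, before database lock.
2. Retitle Listing 16.2-2.3.2 so that it matches Table 14.2-3.2 and refers to reduced urine output rather than retention.
3. Reconcile the hypotension wording across the protocol synopsis, protocol 7.2, protocol 11.1 and the SAP, so that one rule applies throughout. The sponsor should decide which rule and give the reason; this review does not choose it.

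The cost is a wording change, a small number of queries on low-output AEs, and slightly fewer events in both endpoints.
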